### 5.3. Methods to Manage Missing Data

#### 5.3.1. Pharmacokinetic Data

Methods to handle missing PK data are described below.

#### **Concentrations Below the Limit of Quantification:**

In all data presentations (except listings), concentrations below the limit of quantification (BLQ) will be set to zero. In listings, BLQ values will be reported as "<LLQ", where LLQ will be replaced with the value for the lower limit of quantification.

### **Deviations, Missing Concentrations and Anomalous Values:**

In summary tables and plots of median profiles, statistics will be calculated having set concentrations to missing if one of the following cases is true:

- 1. A concentration has been collected as ND (ie, not done) or NS (ie, no sample).
- 2. A deviation in sampling time is of sufficient concern or a concentration has been flagged anomalous by the pharmacokineticist.

Note that summary statistics will not be presented at a particular time point if more than 50% of the data are missing.

An anomalous concentration value is one that, after verification of bioanalytical validity, is grossly inconsistent with other concentration data from the same individual or from other participants. For example, a BLQ concentration that is between quantifiable values from the same dose is considered as anomalous. Anomalous concentration values may be excluded from PK analysis at the discretion of the PK analyst.

#### **PK Parameters:**

Actual PK sampling times will be used in the derivation of PK parameters. If a PK parameter cannot be derived from a participant's concentration data, the parameter will be coded as NC (ie, not calculated). (Note that NC values will not be generated beyond the day that a participant discontinues).

In summary tables, statistics will not be presented for a particular treatment group if more than 50% of the data are NC. For statistical analyses, PK parameters coded as NC will also be set to missing, and statistics will be presented for a particular treatment with >3 evaluable measurements.

If an individual participant has a known biased estimate of a PK parameter (due for example to a dosing error or an unexpected event such as vomiting before all the compound is adequately absorbed from the gastrointestinal tract), this will be footnoted in summary tables and will not be included in the calculation of summary statistics or statistical analyses. For instance, if a participant has a vomiting event post dose that is within a duration of time that is 2-times the derived median  $T_{max}$  for the population for the administered treatment, then the pharmacokineticist should consider the exclusion of the PK concentration data collected following the initial vomiting event in that treatment period and the PK parameter data reported for that treatment period from the datasets used to calculate summary statistics or statistical analyses.

PFIZER CONFIDENTIAL DMB02-GSOP-RF02 8.0 *Statistical Analysis Plan Template* TMF Doc ID: 98.03 Page 9 of 16

## 5.3.2. Safety Data

Missing values in standard summaries of safety data will be imputed according to CaPS.

### 6. ANALYSES AND SUMMARIES

#### 6.1. Primary Endpoints

Plasma AUC24hr, AUC24hr-last, AUClast, AUCinf and  $C_{max}$  of etrasimod will be summarized by treatment group and will include the set of summary statistics as specified in Table 3.

Parameter	Summary Statistics
AUC 24hr , AUC 24hr last, AUC inf , AUC last , C max	N, arithmetic mean, median, SD, %CV, minimum, maximum, geometric mean and geometric %CV

Natural log transformed AUC24hr, AUC24hr-last, AUCinf, AUClast, and Cmax will be analyzed using a mixed effect model with treatment as a fixed effect and participant as random effect. Estimates of the adjusted mean differences (Test-Reference) and corresponding 90% CIs will be obtained from the model. The adjusted mean differences and 90% CIs for the differences will be exponentiated to provide estimates of the ratio of adjusted geometric means (Test/Reference) and 90% CI for the ratios. Treatment F (etrasimod 2 mg, DCT Tasso PK micro samples taken by CRU staff and participants) will be the Reference treatment while Treatment G (etrasimod 2 mg, DCT Tasso PK micro samples taken by participants only) will be the Test treatment.

A listing of the individual participant ratios (Test/Reference) will be provided. Box and whisker plots for  $AUC_{24hr}$ ,  $AUC_{24hr-last}$ ,  $AUC_{inf}$ ,  $AUC_{last}$  and  $C_{max}$ , will be plotted by treatment and overlaid with geometric means.

Residuals from the models will be examined for normality and the presence of outliers via visual inspection of plots of residuals vs predicted values and normal probability plots of residuals but these will not be included in the CSR. If there are major deviations from normality or outliers then the effect of these on the conclusions will be investigated through alternative transformations and/or analyses excluding outliers. Justification for any alternative to the planned analysis will be given in the report of the study.

### 6.2. Secondary Endpoints

### 6.2.1. PK Parameters from Tasso and Venous Blood Sampling

Natural log transformed AUC24hr, AUC24hr-last, AUCinf, AUClast, and Cmax will be analyzed using an ANOVA with treatment as a fixed effect. Estimates of the adjusted mean differences (Test-Reference) and corresponding 90% CIs will be obtained from the model. The adjusted mean differences and 90% CIs for the differences will be exponentiated to provide estimates of the ratio of adjusted geometric means (Test/Reference) and 90% CI for the ratios. Treatment A (etrasimod 2 mg, Main study, venous PK samples) will be the Reference treatment while Treatment F (etrasimod 2 mg, DCT Tasso PK micro samples taken by CRU staff and participants) and Treatment G (etrasimod 2 mg, DCT Tasso PK micro samples taken by participants only) will be the Test treatments.

> PFIZER CONFIDENTIAL DMB02-GSOP-RF02 8.0 Statistical Analysis Plan Template TMF Doc ID: 98.03 Page 10 of 16

### 6.2.2. Safety Endpoints

All safety analyses will be performed on the Safety Analysis Set.

Safety data will be presented in tabular and/or graphical format and summarized descriptively, where appropriate.

#### 6.2.2.1. First Dose HR reduction

Changes from predose baseline in HR at every hour up to 6 hours, at 8 and 24 hours on Day 1 and on Days 3 to 5, as well as the nadir HR value on Day 1 of each period, will be summarized by treatment.

#### 6.2.2.2. Adverse Events

TEAEs will be reported in accordance with the CaPS.

Participant discontinuations due to adverse events will be detailed by treatment. Data will be reported in accordance with the CaPS.

### 6.2.2.3. Laboratory Data

Laboratory data will be listed and summarized by treatment in accordance with the CaPS.

### 6.2.2.4. Vital Signs

Vital sign data will be listed and summarized by treatment in accordance with the CaPS.

#### 6.2.2.5. Electrocardiograms

ECG data will be listed and summarized by treatment in accordance with the CaPS.

Changes from baseline for the ECG parameters will be summarized by treatment. The number (%) of participants with maximum postdose QTcF values and maximum increases from baseline in the following categories will be tabulated by treatment.

Degree of Prolongation	Mild (ms)	Moderate (ms)	Severe (ms)
Absolute value	>450 – 480	>480 - 500	>500
Increase from baseline		30-60	>60

### 6.3. Other Safety Summaries and Analyses Endpoint(s)

None.

### 6.4. Exploratory Endpoint

#### 6.4.1. Plasma Concentrations of Etrasimod

The plasma concentrations will be listed and descriptively summarized by nominal PK sampling time and treatment. Individual participant, as well as mean and median profiles of the plasma concentration-time data will be plotted by treatment using actual (for individual) and nominal (for mean and median) times respectively. Mean and median profiles will be presented on both linear and semi-log scales.

PFIZER CONFIDENTIAL DMB02-GSOP-RF02 8.0 *Statistical Analysis Plan Template* TMF Doc ID: 98.03 Page 11 of 16 Presentations of concentrations will include:

- A listing of all concentrations sorted by participant ID, treatment and nominal time postdose. The concentration listing will also include the actual times. Deviations from the nominal time will be given in a separate listing.
- A summary of concentrations by treatment and nominal time postdose, where the set of statistics will include n, mean, median, SD, %CV, minimum, maximum and the number of concentrations above the LLQ.
- Median concentrations time plots (on both linear and semi-log scales) against nominal time postdose by treatment (all treatments on the same plot per scale, based on the summary of concentrations by treatment and time postdose).
- Mean concentrations time plots (on both linear and semi-log scales) against nominal time postdose by treatment (all treatments on the same plot per scale, based on the summary of concentrations by treatment and time postdose).
- Individual concentration-time plots by treatment (on both linear and semi-log scales) against actual time postdose (there will be separate spaghetti plots for each treatment per scale).
- Individual concentration-time plots by participant (on both linear and semi-log scales) against actual time postdose [there will be separate plots for each participant (containing all treatments) per scale].

Etrasimod concentrations at the predose and 2- and 4-hour postdose sampling time points from paired samples obtained via micro sampling and venous sampling will be compared. Individual participant differences and % differences of concentrations by PK sampling time, will be listed and summarized descriptively.

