Study intervention administration			X					Participants assigned to receive study intervention under fasted must be fasted for at least 10 hours pre dosing and 4 hours postdosing.
								See Section 6.1.1 for additional details

 Table 1.
 Study Schedule of Assessment

Visit Identifier Abbreviations used in this table may be found in Appendix 10	Screen		Per	iods 1-2		F/U Telephone Contact	ET	Notes
Days Relative to Day 1 in Each Period	Day -28 to Day -2	Day -1	Day 1	Day 2	Days 3-8	Days 28-35*		 Participants will be screened within 28 days of the first dose of study intervention. * Follow-up contact will occur by telephone and must occur at least 28 to 35 days after the last administration of etrasimod (Day 1 of Period 2 if dosing completed).
Period 1 Study Days	-28 to -2	-1	1	2	3-8			Participants will be discharged from CRU on Day 2 of Period 1
Period 2 Study Days		9	10	11	12-17			 Minimum 8-day washout period between dosing in Periods 1 and 2 Participants will be discharged from CRU on Day 2 of Period 2.
PK blood sampling (Periods 1 and 2)			X				X	Venous PK sample blood collection (for Tasso results comparison) will be at the following timepoints: predose and at 2 and 4 hours postdose.
PK micro sampling (Periods 1 and 2)			X	X	X			 Micro sampling PK sample collection will be on the day of dosing at the following timepoints: predose and at 1, 2, 4, 6, 8, 12, 24, 48, 72, 96, 120, 144, and 168 hours postdose Micro PK sampling for Period 1 (Treatment F) will be performed by CRU staff up to 24 hours postdose (at CRU) and by the participants 48-168 hours post dose (remote) Micro PK sampling for Period 2 (Treatment G) will be performed by the participants at the CRU (up to 24 hours postdose) and remote (48-168 hours postdose) Micro PK sampling occurs after venous PK blood sampling; samples to be taken from the alternate arms from one sampling time to the next.

 Table 1.
 Study Schedule of Assessment

Visit Identifier Abbreviations used in this table may be found in Appendix 10	Screen		Peri	iods 1-2		F/U Telephone Contact	ET	Notes
Days Relative to Day 1 in Each Period	Day -28 to Day -2	Day -1	Day 1	Day 2	Days 3-8	Days 28-35*		 Participants will be screened within 28 days of the first dose of study intervention. * Follow-up contact will occur by telephone and must occur at least 28 to 35 days after the last administration of etrasimod (Day 1 of Period 2 if dosing completed).

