### 2.2. Study Objectives, Endpoints, and Estimands

The following are the objectives and endpoints in this study. Estimand framework will not be applied to this Phase 1 study in healthy participants.

Objectives	Endpoints	
Primary:	Primary:	
• To compare the PK of etrasimod 2 mg clinical IR tablets under fasted conditions in healthy participants using Tasso OnePlus PK micro samples taken by participants only (Treatment G) vs. CRU staff and participants (Treatment F) in a hybrid DCT design	
 
Plasma AUC24hr, AUC24hr-last, AUCinf (if data permit, otherwise AUClast) and Cmax of etrasimod
 
	
Secondary:	Secondary:	

 
To compare the PK of etrasimod 2 mg clinical IR tablets under fasted conditions in healthy participants using Tasso OnePlus PK micro samples taken by participants only (Treatment G) vs. CRU staff and participants (Treatment F) in a hybrid DCT design vs. venous PK samples taken by CRU staff in conventional design of main study (Treatment A)
 
	
 
Plasma AUC24 hr, AUC24hr-last, AUCinf (if data permit, otherwise AUClast) and Cmax of etrasimod
 
	

 
To evaluate the safety and tolerability of etrasimod 2 mg clinical IR tablets in healthy participants using mobile wearable devices in a hybrid DCT design
 
	
 
Assessment of first dose HR reduction, TEAEs, clinical laboratory abnormalities, vital signs, PEs, and ECGs
 
	
Tertiary/Exploratory:	Tertiary/Exploratory:	

 
To compare the concentrations of etrasimod in PK samples collected using Tasso OnePlus micro sampling device against those using venous blood sampling.
 
	• Plasma concentrations of etrasimod obtained via micro sampling compared to venous sampling at pre-dose and at 2 and 4 hrs post-dose.	

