# 2.3. Study Design

This is a Phase 1, open-label, single-dose, fixed-sequence, crossover study in a single cohort of approximately 8 healthy male or female participants conducted using a hybrid DCT design.

The study will consist of 2 treatments. Participants will receive the two Treatments F and G in a fixed sequence as shown below. There will be an 8-day washout between each dose.

Fixed Treatment Sequence (n=8)	Period 1	Period 2
1	F	G

Treatment F: Single oral dose of etrasimod 2 mg, DCT with practice sessions\* (Reference)

Treatment G: Single oral dose of etrasimod 2 mg, DCT without practice sessions\*\* (Test)

\* Practice of Tasso and Wearable Monitoring Devices on Day 2 at CRU; participant self-assessment remotely for vitals and ECG (Days 3-5) and PK samples (Days 3-8)

\*\* Participant self-assessment using Tasso and Wearable Monitoring Devices on Days 1-2 at CRU; and remotely on Days 3-8

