### 3.4. Exploratory Endpoint

Plasma concentrations of etrasimod obtained via micro sampling (taken by participants only and taken by CRU staff and participants) compared to venous sampling at predose and at 2 and 4 hours postdose.

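### The paired Tasso–venous samples are only to be summarised descriptively; a by-treatment ratio and a paired G-minus-F contrast would be a cheap exploratory check on the Day 1 part of the fixed-sequence G/F comparison

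*SAP*

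**What the plan says.** The exploratory objective in SAP 2.2 is "To compare the concentrations of etrasimod in PK samples collected using Tasso OnePlus micro sampling device against those using venous blood sampling". SAP 3.4 defines the endpoint by who collected the sample: "Plasma concentrations of etrasimod obtained via micro sampling (taken by participants only and taken by CRU staff and participants) compared to venous sampling". For the analysis, SAP 6.4.1 states "Individual participant differences and % differences of concentrations by PK sampling time, will be listed and summarized descriptively", and Protocol 9.3.4 has the same sentence. That sentence names sampling time but not treatment. Other outputs in SAP 6.4.1 do name treatment, for example "A summary of concentrations by treatment and nominal time postdose".

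The Schedule of Activities (Protocol 1.3) provides the comparator in both periods: "Venous PK sample blood collection (for Tasso results comparison) will be at the following timepoints: predose and at 2 and 4 hours postdose". Up to 24 hours, CRU staff take the Tasso samples in Period 1 (F) and participants take them in Period 2 (G). From 48 hours, participants take them in both periods. Each Tasso sample follows the venous draw.

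On design, SAP 2.3 says "Participants will receive the two Treatments F and G in a fixed sequence as shown below". On the primary analysis, SAP 6.1 says each log-transformed parameter "will be analyzed using a mixed effect model with treatment as a fixed effect and participant as random effect".

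**The concern.** The primary question is whether samples collected by participants give the same PK as samples collected partly by staff. With a single sequence, the G/F ratio is the product of any collector effect and any systematic Period 2 versus Period 1 shift in exposure. A period term cannot be estimated, so no change to the primary model would help.

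The venous samples at 2 and 4 hours offer a partial way round. Dividing each Tasso value by its paired venous value removes true exposure on that occasion. Comparing the ratio between G and F within participant then isolates the collector contrast at those times from a period shift in exposure. The plan collects these samples but specifies no estimate that uses them in this way. At stake is a prespecified supportive result to set beside the Day 1 part of G/F (AUC24hr and Cmax). In an open-label study, such a contrast carries less weight if it is chosen after G/F has been seen.

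**Working it through.** **The plan's own precision figures.** Protocol Table 3 is the only statement of precision. At a ratio of 100% it gives 75.44–132.55% for AUC. This reproduces as two independent groups of 8 with 14 df and an 80% coverage factor: 1.761 × 0.281 × √(2/8) × √(18.151/14) = 0.2818, and exp(±0.2818) = 75.44% and 132.55%. Table 3 does not cover the Tasso–venous pairs, so their precision has to be worked out from assumptions.

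**Number of pairs.** 2 postdose times × 2 periods × 8 participants = 32 postdose pairs, or 8 per time and treatment. With predose there are 48.

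**Assumptions.**
- se is the log-scale SD of one measurement, the same for Tasso and venous, with independent errors. The documents give no value; the range 0.05 to 0.30 is assumed.
- sb is an extra participant-by-period SD in the Tasso result. It is 0 unless stated.

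**Formulae.** One ln(Tasso/venous) has variance 2se². Averaging 2 h and 4 h gives se², plus sb². With t(0.95, 7 df) = 1.895:
- ratio for one treatment: half-width = 1.895 × √((se² + sb²)/8)
- paired G-minus-F contrast: half-width = 1.895 × √(2(se² + sb²)/8)

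For se = 0.10, the paired half-width is 1.895 × √(0.02/8) = 1.895 × 0.05 = 0.0947, which gives 91.0–109.9%.

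| se | Ratio for F or G, 90% CI | G-minus-F, 90% CI | P(CI excludes 100%) if the true contrast is 90% |
|---|---|---|---|
| 0.05 | 96.7–103.4% | 95.4–104.9% | 0.98 |
| 0.10 | 93.5–106.9% | 91.0–109.9% | 0.60 |
| 0.20 | 87.5–114.3% | 82.7–120.9% | 0.25 |
| 0.30 | 81.8–122.3% | 75.3–132.9% | 0.17 |

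Intervals are centred on 100%. The last column uses the noncentral t distribution with 7 df. The by-treatment intervals widen if participants differ in their underlying Tasso/venous ratio; the paired contrast removes a constant difference of that kind.

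**Sensitivity.** With se = 0.10 and sb = 0.15, the paired interval is 84.3–118.6% and the probability falls to 0.28. With 6 evaluable participants (5 df, t = 2.015), se = 0.10 gives 89.0–112.3% and se = 0.30 gives 70.5–141.8%.

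**What the contrast adds.** As an illustration with assumed values, let self-collection read 10% low and let Period 2 exposure be 10% higher. Then Tasso G/F at these times is 0.90 × 1.10 = 0.99, while the venous-paired contrast is 0.90. A simulation with n = 8, occasion-to-occasion SD 0.15 and SD 0.10 for ln(Tasso/venous) gave 0.99 and 0.90. The nominal 90% CI for G/F covered the true collector ratio about 72% of the time, against about 90% for the contrast.

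**The case against.** A reader might infer that the plan will pool F and G pairs and so hide a collector effect: 100% in F and 90% in G would pool to √(1.00 × 0.90) = 94.9%. The documents do not support that. No section says the pairs will be pooled, SAP 3.4 separates the collectors, and the surrounding summaries are by treatment. A by-treatment display is at least as natural a reading.

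A reader might also infer that a period shift would go unseen. That is too strong. SAP 6.4.1 lists all concentrations by participant, treatment and time, lists the individual paired differences, and summarises concentrations by treatment. Venous values under F and G can therefore be compared informally. Nor do the documents show any shift: the tablet and fasting conditions are the same in both periods, and carryover is small (192 to 216 hours is 6.4 to 7.2 half-lives of 30 hours, leaving 1.2% to 0.7%).

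It can fairly be added that the objective asks only for Tasso versus venous, that Protocol 8.5 calls the venous samples exploratory, that no hypothesis is tested, and that the contrast is imprecise unless assay and sampling error are small. All of this stands, and it limits the point to an optional addition. It does not remove the remaining gap: no planned estimate with a CI separates collector from period, although samples that can partly do so are already being taken.

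**Conclusion.** The point holds as a low-cost exploratory improvement. It is not an error in the plan. By-treatment ratios and a paired contrast are more informative than a descriptive table of differences, because they remove period effects on true exposure that the G/F model cannot separate from collector.

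The contrast would be an estimate with a CI, not a reliable test: from 95–105% to 75–133% over the assumed SD range with 8 evaluable participants. Its limits are:
- It covers 2 of the 14 Tasso times. These are close to the 4-hour median Tmax, but an individual Cmax may fall elsewhere.
- It says nothing about AUC24hr-last, because participants take the later samples in both periods.
- Period-specific effects of device, handling or assay run remain in it.
- Because Tasso follows the venous draw, a longer delay in self-collection could look like a collector effect at 2 hours, when concentrations are typically still rising.

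It should not be used to adjust any AUC or Cmax estimate.

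**What to change.** In SAP 6.4.1, labelled exploratory, and with the wording in item 1 mirrored in Protocol 9.3.4:

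1. Summarise the paired differences by treatment and PK sampling time, consistent with SAP 3.4.
2. For each participant and period, average ln(Tasso/venous) over 2 h and 4 h. Report the geometric mean ratio with 90% CI for F and for G.
3. Report the within-participant G-minus-F contrast of that average with a paired 90% CI (7 df if all 8 participants are evaluable).
4. Show the actual Tasso and venous sampling times beside the ratios.
5. State that the result is a supportive check on the Day 1 part of G/F, with the limits above, and not a correction of the primary estimates.

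The cost is one exploratory table. It needs no extra samples or participants and no change to study conduct or the primary analysis.

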### 6.5. Subset Analyses

There are no planned subset analyses.

#### 6.6. Baseline and Other Summaries and Analyses

#### 6.6.1. Demographic Summaries

Demographic characteristics will be summarized for Safety Analysis Set in accordance with the CaPS.

### 6.6.2. Study Conduct and Participant Disposition

Participants evaluation groups will show end of study participant disposition. Frequency counts will be supplied for participant discontinuation(s) by treatment. Data will be reported in accordance with the CaPS.

